9.2.4 Power

Power will be calculated as per section 9.2.1 and will be reported for CmaxSS and AUC(0-r)SS.

9.2.5 Two one-sided tests for bioequivalence

90% (if power is more than 80% at stage 1) & 94.12% (as applicable, if the power is less than 80% at stage 1 and stage 2) confidence intervals for the difference between least squares means of test and reference formulations will be calculated using mean square error, obtained in ANOVA, for ln-transformed C_{maxSS} and $AUC_{(0-\tau)SS}$. 90% (if power is more than 80% at stage 1) & 94.12% (as applicable, if the power is less than 80% at stage 1 and stage 2) confidence interval for the geometric least squares means ratio will be obtained by taking the exponent of lower and upper limits of 90% (if power is more than 80% at stage 1) & 94.12% (as applicable, if the power is less than 80% at stage 1) & 94.12% (as applicable, if the power is less than 80% at stage 1) & 94.12% (as applicable, if the power is less than 80% at stage 1) & 94.12% (as applicable, if the power is less than 80% at stage 1) and stage 2) confidence interval, obtained for the least squares means difference.

Two one-sided test, namely Schuirmann's test, will be employed at 5% level of significance for the

Page 23 of 30

lower and upper limits of 90% (if power is more than 80% at stage 1) & 94.12% (as applicable, if the power is less than 80% at stage 1 and stage 2) confidence interval to check whether the 90% (if power is more than 80% at stage 1) & 94.12 (as applicable, if the power is less than 80% at stage 1 and stage 2) confidence interval for C_{maxSS} and $AUC_{(0-\tau)SS}$ will be entirely within the bioequivalence limits of 80.00% to 125.00%.

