Pharmacokinetic and Statistical Methods	Pharmacokinetic and statistical analysis will be performed at  Using the concentration time profile of Olaparib, the following pharmacokinetic parameters will be computed and reported:
	Primary variables: C maxSS and AUC (0-4)SS
	Secondary variables: C minSS , T maxSS , C avSS , swing and percentage of fluctuation.
	ANOVA, least squares means for test and reference formulations, difference between test and reference formulations, intra-subject variability and power will be calculated for ln-transformed pharmacokinetic parameters C maxSS and AUC (0-1)SS . Geometric least squares means of test and reference formulations, T/R ratio, 90% confidence interval for geometric least squares means ratio and Two One-Sided Tests for 90% confidence interval limits will be calculated for pharmacokinetic parameters C maxSS and AUC (0-1)SS .
 	By considering the three day's morning pre-dose concentrations in a given period,

Confidential Page 23 of 91

steady state analysis will be performed for each subject in each period by using the linear regression analysis to obtain the p-values. The above analyses will be done using procedure PROC REG in SAS, version 9.4 or higher.

For achieving the steady state following procedure should be assessed:

Step 1: For each subject in each period the P-values should be statistically insignificant at 5% level of significance.

If, P-values are found statistically insignificant, those patients are considered to achieve steady state. If, P-values are found significant for particular subject then go for the second step. Go for second step for patients who have missing pre-dose sample for Day 6 or Day 14.

Step 2: Ratio of the pre-dose concentrations of last two pre-dose should be  $\geq 80.00\%$  or should be  $\leq 120.00\%$ .

In case ratio of last two pre-dose concentrations is found to be  $\geq 80.00\%$  or  $\leq 120.00\%$  patients will be considered to achieve steady state. If two pre-dose concentrations is found to be less than 80.00% or greater than 120.00%, patients will not be considered to achieve steady state and will be removed from bioequivalence evaluation.

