### 15.2.3 Two one-sided tests for bioequivalence

90% (if power is more than 80% at stage 1) & 94.12% (as applicable, if the power is less than 80% at stage 1 and stage 2) confidence intervals for the difference between least squares means of test and reference formulations will be calculated using mean square error, obtained in ANOVA, for In-transformed CmaxSS and AUC(0-7)SS. 90% (if power is more than 80% at stage 1) & 94.12% (as applicable, if the power is less than 80% at stage 1 and stage 2) confidence interval for the geometric least squares means ratio will be obtained by taking the exponent of lower and upper limits of 90% (if power is more than 80% at stage 1) & 94.12% (as applicable, if the power is less than 80% at stage 1 and stage 2) confidence interval, obtained for the least squares means difference.

Two one-sided test, namely Schuirmann's test, will be employed at 5% level of significance for the lower and upper limits of 90% (if power is more than 80% at stage 1) & 94.12% (as applicable, if the power is less than 80% at stage 1 and stage 2) confidence interval to check whether the 90% (if power is more than 80% at stage 1) & 94.12 (as applicable, if the power is less than 80% at stage 1 and stage 2) confidence interval for  $C_{maxSS}$  and  $AUC_{(0-t)SS}$  will be entirely within the bioequivalence limits of 80.00% to 125.00%.

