9.2.1 Steps of a two stage design according to Potvin C

Page 20 of 30

Stage 1:

Step1:

Evaluate the power at stage 1 using the variance estimate from stage 1, GMR of 0.95 and an α level of 0.05 for each of C_{maxSS} and AUC_{(0- τ)SS} parameters.

Before proceeding to Step 2, notify the sponsor (via email) regarding stage 1 power and CV values. However, the other BE assessment results (e.g. GMR point estimates or confidence intervals) should not be calculated at Step 1 nor shared with the sponsor. After a confirmatory email is received from the sponsor, proceed to Step 2.

Step 2:

Step 2.1: If power (calculated using the observed variability and GMR of 0.95) is greater than or equal to 80% for both of the parameters (C_{maxSS} and $AUC_{(0-\tau)SS}$), evaluate BE at stage 1 using an α level of 0.05 and stop regardless of whether BE is met or not.

OR

Step 2.2: If the power for either of the two parameters (C_{maxSS} or AUC_{(0- τ)SS}) is less than 80%, evaluate BE using an α level of 0.0294.

Step 2.2.1: If the BE criterion is met, stop.

OR

Step 2.2.2: If the BE criterion is not met, calculate the sample size for stage 2 based on the variance estimated at stage 1, GMR of 0.95 and an α level of 0.0294, round up to nearest even number, add 20% subjects for dropouts and continue to stage 2. If the calculated sample size for stage 2 is less than 12, include at least 12 subjects in stage 2. If the GMR point estimate for any parameter (C_{maxSS} or AUC_{(0-\tau)SS}) is outside 80.00%-125.00% then study will not proceed for stage 2.

Stage 2

Evaluate BE at stage 2 using data pooled from both stages and an α level of 0.0294. Stop here whether BE is met or not and regardless of the power achieved.

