9.2.7 Bioequivalence criteria

For Stage 1 with Power \geq 80%:

Based on the statistical results of 90% confidence intervals for the geometric least squares means ratio for the ln-pharmacokinetic parameters C_{maxSS} and $AUC_{(0-\tau)SS}$ for Olaparib the conclusions will be drawn whether test formulation is bioequivalent to reference formulation under Fasting condition. Acceptance range for bioequivalence is 80.00%-125.00% for 90% confidence intervals of the geometric least squares means ratio of C_{maxSS} and $AUC_{(0-\tau)SS}$.

For Stage 1 with Power < 80% and for Stage 2, if required:

Based on the statistical results of 94.12% confidence intervals for the geometric least squares means ratio for the log-transformed pharmacokinetic parameters C_{maxSS} and $AUC_{(0-\tau)SS}$ for Olaparib the conclusions will be drawn whether test formulation is bioequivalent to reference formulation under Fasting condition. Acceptance range for bioequivalence is 80.00%-125.00% for 94.12% confidence intervals of the geometric least square means ratio of C_{maxSS} and $AUC_{(0-\tau)SS}$.

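### The TOST level is given as 5% for the 94.12% confidence interval as well as the 90% interval; the 94.12% interval corresponds to one-sided 0.0294

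*SAP*

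**What the plan says.** SAP 9.2.5 describes the test in a sentence split by a page break. It begins "Two one-sided test, namely Schuirmann's test, will be employed at 5% level of significance for the" and continues "lower and upper limits of 90% (if power is more than 80% at stage 1) & 94.12", ending with a check that whichever interval applies lies within 80.00% to 125.00%. Protocol 15.2.3 has the sentence unbroken, "Two one-sided test, namely Schuirmann's test, will be employed at 5% level of significance for the lower and upper limits of 90" and onward to the 94.12% interval, so the joint reference is not an artefact of layout. One level, 5%, is attached to both intervals.

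Elsewhere the plan distinguishes two levels:

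- SAP 9.2.1, Step 2.1: with stage 1 power of at least 80% for both parameters, "evaluate BE at stage 1 using an α level of 0.05 and stop regardless of whether BE is met or not".
- SAP 9.2.1, Step 2.2 ("If the power for either of the two parameters" falls below 80%) and stage 2: alpha is 0.0294. Protocol 15.2 gives the same two levels but does not say how two parameters are combined.
- SAP 9.2.7 and Protocol 15.2.6, for those same branches: "Acceptance range for bioequivalence is 80.00%-125.00% for 94.12% confidence intervals of the geometric least square means ratio".

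The Protocol synopsis (Pharmacokinetic and Statistical Methods) says "Two One-Sided Tests for 90% confidence interval limits will be calculated for pharmacokinetic parameters", naming only the 90% interval. The bioequivalence criteria later in the synopsis do include the 94.12% interval.

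**The concern.** Schuirmann's procedure and the confidence-interval check are one decision written two ways, provided that the one-sided level is half the interval's non-coverage. With 5% attached to the 94.12% interval they become different decisions, and the test is the more lenient.

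The affected branches are those where the two-stage design relies on the reduced level. A programmer working from 9.2.5 could output a TOST p-value, compare it with 0.05, and report a pass beside a failed 94.12% interval. The report would then have to explain the conflict. The SAP annex itself says that its simulated type I error is valid only as far as the planned evaluation matches the simulated one, and the simulated design uses 0.0294 here.

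**Working it through.** **1. Level implied by each interval.** One-sided alpha = (1 - confidence level)/2.

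| Interval | Calculation | One-sided alpha | Level in SAP 9.2.5 |
|---|---|---|---|
| 90% | (1 - 0.90)/2 | 0.05 | 5%, correct |
| 94.12% | (1 - 0.9412)/2 | 0.0294 | 5%, incorrect |

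**2. Reproducing the plan's figures.** With n = 56, CV 35%, true ratio 0.95 and alpha 0.05, exact TOST power is 83.5% on 54 df and 83.3% on 44 df, consistent with the stated 81% or more. At alpha 0.0294 it is 76.0% on 54 df. A simulation of the annex design (Nmax 120, point-estimate futility at 0.80 to 1.25, site-adjusted df) gives 86.1% power (annex 86.0%), 9.9% of trials going to stage 2 (annex 9.8%) and mean N 58.2 (annex 3.9% above 56). The 0.0294 design is therefore the one behind the plan's operating characteristics.

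**3. A stage 1 data set on which the two levels disagree.** The annex takes df = n - 2 - (sites - 1) with about five patients per site. For n = 56 that is 11 sites and 56 - 2 - 10 = 44 df. Take an observed CV of 38%.

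- Power at ratio 0.95 and alpha 0.05 is 77.4%, below 80%, so the 94.12% interval governs. The switch occurs at an observed CV of about 36.7%.
- Log-scale variance: ln(1 + 0.38²) = 0.13488. SE = sqrt(2 × 0.13488/56) = 0.06941.
- t quantiles on 44 df: 1.6802 for alpha 0.05 and 1.9400 for alpha 0.0294.
- Observed ratio 0.907: ln(0.907) = -0.09761. Lower-limit statistic: (-0.09761 + 0.22314)/0.06941 = 1.809, p = 0.039. The upper-limit p-value is below 0.0001.
- 90% interval: exp(-0.09761 ± 1.6802 × 0.06941) = 80.72% to 101.92%, a pass.
- 94.12% interval: exp(-0.09761 ± 1.9400 × 0.06941) = 79.27% to 103.77%, a fail.

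**4. Width of the disagreement at this n and CV.** The lower band runs from 0.80 × exp(0.11662) = 0.899 to 0.80 × exp(0.13465) = 0.915. The upper band runs from 1.25 × exp(-0.13465) = 1.093 to 1.25 × exp(-0.11662) = 1.112. Any observed ratio in either band passes a 5% TOST and fails the 94.12% interval.

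**5. Counterfactual only: the 5% test used as the verdict.** No section proposes this. For a single endpoint at true CV 35% and n1 = 56, simulated type I error is about 5.5% (5.4% to 5.6% across simulations without and with the site df adjustment), against 4.8% to 4.9% under the 0.0294 rule. For two endpoints under the either-parameter rule, with one endpoint at true ratio 1.25:

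| CV, tested / other | Other endpoint's ratio | Correlation | 5% as verdict | 0.0294 rule |
|---|---|---|---|---|
| 35% / 35% | 1.0 | 0 | 5.8% | 4.4% |
| 35% / 35% | 1.1 | 0.7 | 5.85% | 4.7% |
| 30% / 40% | 1.0 | 0 | 6.1% | 4.0% |
| 35% / 35% | 1.0 | 0.7 | 4.6% | 3.4% |
| 35% / 35% | 1.25 | 0.7 | 2.3% | 1.8% |

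These runs used 1.5 million trials per scenario. The documents do not give the second endpoint's ratio, CV or correlation, nor which endpoint sets the stage 2 size; it was assumed to be the one with the larger variance.

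**The case against.** The strongest reply is that nothing decisive depends on this sentence. The decision steps and the bioequivalence criteria in both documents use 0.0294 and the 94.12% interval. The sentence itself ends by checking the applicable interval against 80.00% to 125.00%, and a programmer who does that gets the right answer in every branch. A false pass needs a separate p-value compared with 0.05, and SAP 9.2.2 lists no TOST p-value among its outputs. The synopsis line states no level at all; it is incomplete rather than wrong. The type I error figures describe a rule that nobody proposes.

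Most of this stands, and it is why the point is minor and its consequence conditional. It does not rescue the 5%. The section names a test, says it will be employed and assigns it a level. Read purely as an interval check, the level equivalent to the 94.12% interval is still 2.94%. Nor is the branch remote: its threshold, an observed CV of 36.7%, is close to the planning value of 35%. In a single-endpoint simulation at true CV 35% and ratio 0.95, about 31% of trials had stage 1 power below 80%, and the two tests disagreed at stage 1 in about 3%.

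**Conclusion.** The concern holds, as a minor error. SAP 9.2.5 and Protocol 15.2.3 state the wrong TOST level for the 94.12% interval: 5% where one-sided 0.0294 is required. This follows from the interval's definition and needs no assumption.

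If SAP 9.2.7 and Protocol 15.2.6 are followed, bioequivalence decisions, type I error below 5%, power and sample size are unaffected. The practical effect is confined to a TOST result programmed against 5%, which could contradict the governing interval for observed ratios such as 0.899 to 0.915 or 1.093 to 1.112 (n = 56, 44 df, observed CV 38%). The type I error figures are not a forecast for this trial; with two endpoints they depend on unstated inputs and fall on either side of 5%.

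**What to change.** In SAP 9.2.5 and Protocol 15.2.3, replace the single level with: *Schuirmann's TOST at one-sided 0.05 when the 90% CI applies (stage 1 power ≥80% for both parameters) and at one-sided 0.0294 when the 94.12% CI applies (stage 1 power <80% for either parameter, and stage 2).* This also brings 9.2.5, which now says more than 80% and names no parameter, into line with the conditions in SAP 9.2.1.

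Align the synopsis line so that it names both intervals. The cost is one sentence in each document and one synopsis line, with no effect on sample size, conduct or the planned decision rule.

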9.2.6 Ratio Analysis

Geometric least squares means for test and reference formulations will be obtained by taking the exponent of least squares means of test and reference formulations for ln-transformed C_{maxSS} and $AUC_{(0-\tau)SS}$. Ratio will be obtained by taking the exponent of difference of least squares means of test to reference formulations for ln-transformed C_{maxSS} and $AUC_{(0-\tau)SS}$. The comparisons of interest are T vs. R, so the ratios determined will be of the form T/R, where T = Test formulation and R = Reference formulation.

9.2.7 Bioequivalence criteria

For Stage 1 with Power \geq 80%:

Based on the statistical results of 90% confidence intervals for the geometric least squares means ratio for the ln-pharmacokinetic parameters C_{maxSS} and $AUC_{(0-\tau)SS}$ for Olaparib the conclusions will be drawn whether test formulation is bioequivalent to reference formulation under Fasting condition. Acceptance range for bioequivalence is 80.00%-125.00% for 90% confidence intervals of the geometric least squares means ratio of C_{maxSS} and $AUC_{(0-\tau)SS}$.

For Stage 1 with Power < 80% and for Stage 2, if required:

Based on the statistical results of 94.12% confidence intervals for the geometric least squares means ratio for the log-transformed pharmacokinetic parameters C_{maxSS} and $AUC_{(0-\tau)SS}$ for Olaparib the conclusions will be drawn whether test formulation is bioequivalent to reference formulation under Fasting condition. Acceptance range for bioequivalence is 80.00%-125.00% for 94.12% confidence intervals of the geometric least square means ratio of C_{maxSS} and $AUC_{(0-\tau)SS}$.

9.2.8 Clinical Data - CDISC Study Data Tabulation Model

Domains will be mapped to CDISC (Clinical Data Interchange Standards Consortium) SDTM, SDTM IG (Implementation Guide). All versions valid as per FDA Data Standards Catalog will be used for SDTM. No derived data required for analysis will be included in the SDTM domains. The SAP will not be amended to provide information on additional SDTM domains, although this will be allowed if necessary. All SDTM domains will be fully documented with define documents (DEFINE.XML) and a clinical study data reviewer's guide after database lock and final analyses are completed. Validation of CDISC SDTM domains will be done using Pinnacle 21 Community (version 3.1.2 or higher).

9.2.9 Analysis Data - CDISC Analysis Data Model

All planned and exploratory analyses will be completed using the ADaM (Analysis Data Model) data sets (ADaM, ADaM IG) derived from the SDTM domains for this study. All versions valid as per FDA Data Standards Catalog will be used for ADaM. Analysis data sets will contain all derived study endpoints required for analysis. All analysis data sets will be fully documented with define documents (DEFINE.XML) and an analysis data reviewer's guide (ADRG) after database lock and final analyses are completed. Validation of CDISC ADaM domains will be done using Pinnacle 21 Community (version 3.1.2 or higher)

10. Outliers

For outlier identification, appropriate statistical tests could be performed. Outliers are defined as subjects having discordant values of one or more pharmacokinetic parameters when compared with other values, e.g., a subject differs notably from the rest of the subjects for the test product response versus the reference product response. Outlier test will be performed using appropriate statistical method as per **formed** for "Detection of Outliers". Subject data will not be removed from the statistical analysis solely based on the results of statistical outlier tests. Outlier data may only be removed from the statistical analysis if there is a real-time documentation demonstrating a protocol violation during the clinical and/or analytical phase of the BE study.

11. Evaluation of Safety Parameters (Safety Population)

All randomized patients who have received a dose of IMP will be included in safety evaluation. Results obtained when evaluating safety and tolerability (adverse events, vital signs, and clinical laboratory tests) will be listed in the report. AEs occurring prior to first IMP administration will be presented in a separate listing within study report. All AEs will be classified by System Organ Class, Preferred Term (using the Medical Dictionary for Regulatory Activities (MedDRA), version 20.0 or higher), and Severity with respect to treatment received.

11.1. Adverse Events

An adverse event (AE) is any untoward medical occurrence (e.g. any unfavorable and unintended sign [including abnormal laboratory findings], symptom or disease) in a patient or clinical investigation subject after providing written study-specific informed consent for participation in the study. Therefore, an AE may or may not be temporally or causally associated with the use of a medicinal (investigational) product. The investigator has the responsibility for managing the safety of individual subject and identifying adverse events. The occurrence of adverse events must be sought by non-directive questioning of the subject at each visit during the study. Adverse events also may be detected when they are volunteered by the subject during or between visits or through physical examination findings, laboratory test findings, or other assessments.

Any AE (non-serious and serious) occurring after the subject has provided study-specific informed consent and until the last study visit of the subject, has to be recorded on the AE pages of the Case Report Form (CRF).

Medical conditions/diseases present before providing written informed consent are only considered AEs if they worsen after enrolment.

Adverse events (including lab abnormalities that constitute AEs) should be described using a diagnosis whenever possible, rather than individual underlying signs and symptoms. Abnormal laboratory values or test results constitute adverse events only if they fulfill at least one of the following criteria:

- they induce clinical signs or symptoms;
- they are considered clinically significant;
- they require therapy.

Once an adverse event is detected, it must be followed until its resolution or until it is judged to be permanent (e.g. continuing at the end of the study), and assessment must be made at each visit (or more frequently, if necessary) of any changes in severity, the suspected relationship to the interventions required to treat it, and the outcome.

Information about already known adverse drug reactions for the Investigational Medicinal Product drug can be found in the Reference Safety Information (e.g. Prescribing information).

Each adverse event should be evaluated to determine the following:

A. Severity of AEs

Adverse events should be assessed and graded according to the Common Terminology Criteria for Adverse Events (CTCAE) version 5.0. Grade refers to the severity of the AE. The CTCAE version 5.0 displays Grades 1 through 5 with unique clinical descriptions of severity for each AE based on this general guideline.

Grade 1	Mild; asymptomatic or mild symptoms; clinical or diagnostic observations only; intervention not indicated.
Grade 2	Moderate; minimal, local or noninvasive intervention indicated; limiting age-appropriate instrumental ADL*.
Grade 3	Severe or medically significant but not immediately life-threatening; hospitalization or prolongation of hospitalization indicated; disabling; limiting self-care ADL**.

Grade 4	Life-threatening consequences; urgent intervention indicated.
Grade 5	Death related to AE.

*Instrumental ADL (Activities of Daily Living) refer to preparing meals, shopping for groceries or clothes, using the telephone, managing money, etc.

**Self-care ADL refer to bathing, dressing and undressing, feeding self, using the toilet, taking medications, and not bedridden.

B. Relationship to IMP

Adverse event's relationship to the study treatment should be determined (suspected/not suspected). Causality assessments are critical and must be provided for each unique AE in relation to each IMP, non-investigational medicinal product (NIMP) or other concomitant medication, if applicable. Missing causality assessments will be handled as suspected to IMP by the sponsor. The causal relationship between a medicinal product and an adverse event is at least a reasonable possibility, i.e. the relationship cannot be ruled out.

If the event is due to lack of efficacy or progression of underlying illness (i.e. progression of the study indication) the assessment of causality will usually be 'Not suspected.' The rationale for this guidance is that the symptoms of a lack of efficacy or progression of underlying illness are not caused by the trial drug, they happen in spite of its administration and/or both lack of efficacy and progression of underlying disease can only be evaluated meaningfully by an analysis of cohorts, not on a single subject.

C. Evaluation of AEs (duration, action taken, outcome)

The duration (start and end dates) of adverse event should be recorded. Determine whether AE constitutes a serious adverse event (see Section 12.2.2 for definition of SAE) and which seriousness criteria have been met.

Actions taken with respect to investigation medicinal product should be documented as per the below given tabulation using CDISC STDM terminology.

Adverse Event Variable Label	CDISC STDM Terms
Action Taken with the IMP	• Dose increased;
	• Dose not changed;
	 Dose rate reduced;
	 Dose reduced;
	• Drug interrupted;
	 Drug withdrawn;
	 Not applicable;
	 Not known

The outcome of the adverse should be documented and assigned to one of the following categories:

Adverse Event Variable Label	CDISC STDM Terms
Outcome of event	 Not recovered/not resolved; Recovered/resolved;
	• Recovered/resolved with sequelae
	 Recovering/resolving;
	 Fatal; or
	 Unknown.

All AEs must be treated appropriately. The treatment of the AE should be documented in the CRF. Concomitant medication, other non-IMP treatments or changes in the administration of the IMP should be specified and documented. Treatment may include one or more of the following:

- No action taken (i.e. further observation only);
- IMP dosage adjusted/temporarily interrupted;
- IMP permanently discontinued due to this AE;
- Concomitant medication given;
- Non-drug therapy given, patient hospitalized / patient's hospitalization prolonged.

Adverse events should be recorded in the CRF under the signs, symptoms or diagnosis associated with them.

All AEs including both volunteered and the ones considered clinically relevant and reportable as AE by investigator will be recorded in the CRF and in the patient's medical records, irrespective of its association with study medications. Independent /Institutional Ethics Committee (IEC) will be informed regarding AEs as necessary.

Page 28 of 30

The Most Common Adverse Events Associated with Study Medication

- Patients should be carefully monitored for adverse events/toxicity. To manage adverse events such as Myelodysplastic syndrome/Acute myeloid leukemia, Haematological toxicity, Pneumonitis, or Venous Thromboembolic Events, the dose may be reduced or interrupt the treatment.
- To manage adverse reactions, consider interruption of treatment or dose reduction. The recommended dose reduction is 250 mg taken twice daily. If a further dose reduction is required, then reduce to 200 mg taken twice daily.
- Dose adjustment is to be done by the Investigator as per the approved Summary of Product Characteristics, Prescribing Information of Lynparza[®] and the protocol.
- Refer Summary of Product Characteristics and Prescribing Information of Lynparza[®] for further information on management of AEs.

NOTE: If patient requires dose modification (i.e., change from 300 mg twice daily) or dose interruption during study participation, the patient should be withdrawn from the study.

